# 4.1.4 Dose Modification and ADRs Requiring Treatment Discontinuation

#### 4.1.4.1 Dose Modification

The dose of M7824 is 1200mg. Further details about discontinuation, withholding and restarting M7824 based on ADRs and AEs are presented in further detail in Section 5.5.3.

# 4.1.4.2 Adverse Drug Reactions Requiring Treatment Discontinuation

# The following ADRs, defined as any AE assessed as related to M7824 by the Investigator and / or Merck/EMD Serono, require permanent treatment discontinuation:

Any Grade 4 ADRs require treatment discontinuation except for single laboratory values out of normal range that do not have any clinical correlate, and resolve to Grade  $\leq 1$  or Baseline grade within 14 days with adequate medical management.

#### Any Grade 3 ADRs require treatment discontinuation except for any of the following:

- Transient (≤ 6 hours) Grade 3 flu-like symptoms or fever, which is controlled with medical management.
- Transient ( $\leq 24$  hours) Grade 3 fatigue, local reactions, headache, nausea, emesis that resolves to  $\leq$  Grade 1 or Baseline grade.
- Tumor flare phenomenon defined as local pain, irritation, or rash localized at sites of known or suspected tumor.
- Any Grade ≥ 3 drug-related amylase or lipase abnormality that is not associated with symptoms or clinical manifestations of pancreatitis. The study principal investigator should be consulted for such Grade ≥ 3 amylase or lipase abnormalities. If the amylase or lipase abnormality not associated with symptoms or clinical manifestations of pancreatitis has not resolved to Grade ≤ 1 within the subsequent 2 doses (28 days), the subject should permanently discontinue treatment with M7824.
- Grade 3 Hgb decrease (< 8.0 g/dL) that is clinically manageable with blood transfusions or erythroid growth factor use does not require treatment discontinuation.
- Increases in Eastern Cooperative Oncology Group performance status (ECOG PS) ≥ 3 that resolves to ≤ 2 by Day 1 of the next cycle (infusions should not be given if the ECOG PS is ≥ 3 on the day of IMP administration and should be delayed until ECOG PS ≤ 2).

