#### Any Grade 2 ADR should be managed as follows:

- If a Grade 2 ADR resolves to Grade  $\leq$  1 by the last day of the current cycle, treatment may continue.
- If a Grade 2 ADR does not resolve to Grade ≤ 1 by the last day of the current cycle but it is manageable and / or not clinically relevant, the ADR should be discussed with the principal investigator and based upon discussion it is possible the infusion will be given on the following cycle. If at the end of the following cycle, the event has not resolved to Grade 1, discussion should be had with the principal investigator about permanently discontinuing treatment with M7824.

- Upon the second occurrence of the same Grade 2 ADR in the same subject (except for fatigue and hormone insufficiencies that can be managed by replacement therapy), continuation of treatment with M7824 has to be discussed with the principal investigator and might be permanently discontinued.
- Infusion-related reactions and hypersensitivity reactions (Grades 1 to 4) should be handled according to the guidelines provided in Sections **5.5.3.1 and 5.5.3.2**, respectively.
- Anemia should be handled according to the guidelines provided in Section **5.5.3.4**.

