#### 5.5.3.1 Infusion-related reactions

IRRs are defined as any signs or symptoms experienced by participants during the infusion of pharmacologic or biologic agents or any event occurring during or within 1 day of drug administration. IRRs are common ADRs with monoclonal antibodies timely related to drug administration and have been reported as anaphylaxis, anaphylactoid reactions, and cytokine release syndrome, among other terms used. IRRs are important identified risks (adverse reactions) for M7824, and the precautions and management are provided in Table 46

A. Signs and symptoms of infusion related reactions (IRRs) including hypersensitivity include but not limited to pyrexia, chills, flushing, hypotension, dyspnea, wheezing, back pain, abdominal pain, and urticaria, were reclassified as important identified risks (adverse reactions).

B. Management

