# Table 6: Treatment Modification for Symptoms of Infusion-related Reactions Caused byM7824

NCI-CTCAE Grade	Treatment Modification for M7824

 
Grade 1 – mild
 
Mild transient reaction; infusion interruption not indicated intervention not indicated.
 
	
 
Decrease the M7824 infusion rate by 50% and monitor closely for any worsening.
 

	• The total infusion time for M7824 should not exceed 120 minutes

 
Grade 2 – moderate
 
Therapy or infusion interruption indicated but responds promptly to symptomatic treatment (for example, antihistamines, NSAIDs, narcotics, IV fluids); prophylactic medications
 
	
 
Stop M7824 infusion.
 
Resume infusion at 50% of previous rate once infusion-related reaction has resolved or decreased to at least Grade 1 in severity, and monitor closely for any worsening
 

 
Grade 3 or Grade 4 – severe or life-threatening
 
Grade 3: Prolonged (for example, not rapidly responsive to symptomatic medication and / or brief interruption of infusion); recurrence of symptoms following initial improvement; hospitalization indicated for clinical sequelae.
 
Grade 4: Life-threatening consequences;
 
	
 
Stop the M7824 infusion immediately and disconnect infusion tubing from the subject.
 
Subjects have to be withdrawn immediately form M7824 treatment and must not receive any further M7824 treatment
 

IV = intravenous; NCI-CTCAE = National Cancer Institute – Common Terminology Criteria for Adverse Event; NSAIDs = nonsteroidal anti-inflammatory drugs

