#### Table 7: Required Laboratory Panel Tests

ACTH=adrenocorticotropic hormone; ANA=antinuclear antibody; IMP=Investigational Medicinal Product; PCR = polymerase chain reaction; RF=rheumatoid factor; TSH=thyroid-stimulating hormone; T4=free thyroxine.

\*\* Only in case of anemia onset assessed as related to study treatment

+Only day 1 of every cycle

**\*\*\***Only at pre-screening evaluation (see schedule of assessments)

a If hepatitis B surface antigen positive and hepatitis B core antibody positive, then reflex to quantitative HBV DNA (PCR); if hepatitis B core antibody positive alone, then reflex to quantitative hepatitis B DNA (PCR); if hepatitis C antibody positive, then reflex to quantitative hepatitis C RNA (PCR).

If a subject has a clinically significant abnormal laboratory test value that is not present at Baseline, the test will be repeated weekly and the subject will be followed until the test value has returned to the normal range or the Investigator has determined that the abnormality is chronic or stable.

For **pharmacokinetic assessment of M7824**, a blood sample should be collected prior to infusion of M7824 and following completion (within 30 minutes) of infusion of M7824 (doses 1 and 3), prior to dose 2, and prior to dose 6/end of treatment visit (whichever of these two comes first). Samples should be processed as follows:

- 1. Collect 3.5 mL of blood in an SST tube with silica clot activator and polymer gel.
- 2. Gently invert the tube 5 times to mix the clot activator with the blood.
- 3. Allow blood to clot for 30 minutes at room temperature in a vertical position.
- 4. After allowing clot to form, centrifuge the tube for 15 minutes at 1100-1300x g at 25°C. If refrigerated centrifuge is available, set the temperature at 25°C in order to prevent heating during centrifugation and to optimize flow of the barrier material. Flow may be impeded if chilled before or during centrifugation.
- 5. Carefully collect and aliquot the serum equally into 2 separate Micronics tubes.
- 6. Place the tubes immediately into the freezer in an upright position at -80°C.
- 7. Samples will be analyzed as a batch with EMD Serono at a later date.

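### Section 4.1.4.2 sets two different limits for permanent discontinuation after an asymptomatic Grade 4 amylase or lipase rise, and they give opposite outcomes in three identifiable situations

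*Combined protocol and SAP*

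**What the plan says.** Three parts of the combined protocol and SAP bear on this event.

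- **Section 4.1.4.2, Grade 4 paragraph.** It covers events judged related to M7824: "Any Grade 4 ADRs require treatment discontinuation except for single laboratory values out of normal range that do not have any clinical correlate". The exception has a further condition, resolution to Grade 1 or below "or Baseline grade within 14 days with adequate medical management".
- **Section 4.1.4.2, Grade 3 exceptions.** One bullet exempts "Any Grade ≥ 3 drug-related amylase or lipase abnormality that is not associated with symptoms or clinical manifestations of pancreatitis". The principal investigator should be consulted. If the value has not come down to Grade 1 or below "within the subsequent 2 doses (28 days), the subject should permanently discontinue treatment with M7824". Baseline grade is not mentioned.
- **Table 7 (section 6.4.3) and section 6.1.2.** The footnote for amylase and lipase reads "Only day 1 of every cycle", and section 6.1.2 sets a cycle at 28 days. Below Table 7, weekly repeats are required only when a new abnormality is clinically significant.

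A secondary overlap concerns infusion-related reactions. The same Grade 3 list exempts fever or flu-like symptoms lasting up to 6 hours, and fatigue, local reactions, headache, nausea or emesis lasting up to 24 hours. Section 5.5.3.1 defines an infusion-related reaction to include "any event occurring during or within 1 day of drug administration". For Grade 3 or 4 reactions, Table 6 says that subjects "must not receive any further M7824 treatment". A bullet under the Grade 2 heading of 4.1.4.2 says: "Infusion-related reactions and hypersensitivity reactions (Grades 1 to 4) should be handled according to the guidelines" in 5.5.3.1 and 5.5.3.2.

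**The concern.** The amylase/lipase bullet stands in the Grade 3 list but is worded to reach Grade 4, which the preceding paragraph already governs. The two rules differ in three respects: the time allowed (14 against 28 days), the resolution target (Grade 1 or Baseline grade, against Grade 1 only) and the scope (a single laboratory value, against any amylase or lipase abnormality). Discontinuation is permanent, so two investigators who follow the text faithfully could treat the same patient in opposite ways.

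What is at stake is the exposure and safety handling of individual patients in cohorts of 15, 29 and 15. The tabulation of premature terminations by primary reason (section 7.5.3.1) would also depend on which paragraph was applied.

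**Working it through.** No sample size, power or error rate is involved. The check sets the two rules side by side for an asymptomatic, drug-related Grade 4 rise, counting days from the abnormal value. The 28-day figure is consistent with the dosing interval: 2 doses × 14 days = 28 days.

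| Course of the rise | Grade 4 paragraph | Amylase/lipase bullet | Result |
|---|---|---|---|
| One enzyme, Grade ≤ 1 by day 14 | stays on | stays on | agree |
| One enzyme, not at Grade ≤ 1 or Baseline grade by day 14, reaches Grade ≤ 1 on days 15–28 | off | stays on | **conflict (i)** |
| Both enzymes at Grade 4, both Grade ≤ 1 by day 28 | off, if two enzymes are not a single value | stays on | **conflict (ii)** |
| Returns by day 14 to a Baseline grade above 1, never reaches Grade ≤ 1 | stays on | off | **conflict (iii)** |
| Not at Baseline grade by day 14 and not Grade ≤ 1 by day 28 | off | off | agree |

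Conflict (iii) runs in the opposite direction to (i) and (ii). It needs a Baseline grade above 1. The entry criteria leave that open: section 4.3.1 sets no amylase or lipase limit, and exclusion 13 in section 4.3.2 concerns only persisting toxicity from earlier cancer therapy.

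*Test schedule.* Consecutive scheduled tests are nominally 28 days apart. A rise found on Day 1 of one cycle is next tested, on schedule, at day 28, so nothing falls inside a 14-day limit. The ±7-day visit window brings two tests to 28 − 7 − 7 = 14 days apart only if the first is as late and the second as early as allowed. The weekly repeats would fill the gap, but only if the value is called clinically significant, and a rise without symptoms or clinical correlate may not be.

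*Frequency.* Table 5 lists every Grade 4 or higher event in the 32 colorectal patients given 1200 mg, related or not, and shows no amylase or lipase event. Sections 2.1.1 and 2.2.4 report no related Grade 4 or 5 event there. Zero of 32 has an exact two-sided 95% upper limit of 1 − 0.025^(1/32) = 10.9%, so the event looks uncommon but its rate is poorly known. This assumes that the enzymes were measured and reported as adverse events in that cohort. The conflicts arise in only a part of such events.

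*Infusion-related reactions.* Table 6 describes Grade 3 as prolonged, recurring after initial improvement, or with hospitalization indicated. A reaction that responds promptly to symptomatic treatment is its Grade 2, for which the infusion may resume. Two situations within a day of dosing remain unclear. In one, a symptom falls within the 6- or 24-hour limit but responds slowly, recurs or leads to hospital care. In the other, the symptom's own CTCAE grade is 3 although Table 6 would call the reaction Grade 2.

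**The case against.** The best defence is that the specific rule displaces the general one. The amylase/lipase bullet names the abnormality, states its own grade range and time limit, and brings in the principal investigator. That is a reasonable way to read it, but the text does not say so. The Grade 4 paragraph has its own laboratory exception and does not refer to the bullet, while the bullet sits under a Grade 3 heading. Confining it to Grade 3 is no easier, because it writes Grade ≥ 3 twice. Assuming that the stricter rule governs does not identify one paragraph either, since conflict (iii) reverses which is stricter. Consultation is required, but the principal investigator is given no rule to apply.

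The defence also limits the point, and this stands. The two rules agree in the other courses in the table. The trial runs at one institution (section 1), so differences between sites are not the issue. Patients in cohorts A-C and B who stop for toxicity continue imaging until progression (sections 4.1.1.1 and 4.1.1.2), and all treated patients stay in the response denominator (section 7.5.2.1.1).

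A reader might go further and infer that the infusion-reaction definition voids the brief Grade 3 exceptions, so that the same patient is both kept on and taken off. The documents do not support that. Section 4.1.4.1 refers discontinuation details to 5.5.3, the routing bullet covers Grades 1 to 4, and Table 6's description of Grade 3 leaves out many brief, promptly controlled reactions.

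Nor can the size of that overlap be projected from the Grade ≥ 3 nausea, vomiting, fatigue, pyrexia and headache entries in Table 5. Those counts are of any cause, whereas 4.1.4.2 covers related events only. The related Grade 3 events in that cohort were anemia, raised bilirubin, enteritis and adrenal insufficiency, one each, and none of the 5 infusion-related reactions was Grade 3 or higher. Timing and duration are not given.

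**Conclusion.** The inconsistency within 4.1.4.2 is real but narrow. For an asymptomatic, related Grade 4 amylase or lipase rise, the section gives opposite permanent outcomes in conflicts (i) to (iii), with no stated precedence. Conflict (ii) assumes that two raised enzymes are not a single laboratory value, and conflict (iii) assumes a Baseline grade above 1. The 14-day limit cannot be checked at the nominal test times. The expected frequency is low or unknown, so the case rests on contradictory instructions for an irreversible decision, not on a predicted number of patients. The passages should be reconciled.

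The infusion-reaction overlap is a secondary clarification. The text implies that 5.5.3.1 governs, but it does so in a bullet under the Grade 2 heading and leaves open which grading applies. Which clinical rule is right in either case is for the sponsor, and no view is taken here.

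**What to change.** 1. Reconcile the Grade 4 paragraph and the amylase/lipase bullet in 4.1.4.2 so that one time limit and one resolution criterion apply to asymptomatic Grade 4 amylase or lipase. State whether a return to Baseline grade counts, and whether a rise in both enzymes is a single laboratory value.
2. Make the amylase and lipase schedule in Table 7 consistent with the limit that the sponsor keeps, so that it can be verified without depending on whether the value is called clinically significant.
3. As a clarification, reconcile the brief Grade 3 exceptions and the routing bullet in 4.1.4.2 with the definition in 5.5.3.1 and with Table 6. State which rule governs and which grading is used, and place the routing where it plainly applies to all grades.

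The cost is a few sentences in 4.1.4.2 and 5.5.3.1 and possibly a changed footnote to Table 7. The only operational burden is an occasional repeat amylase or lipase test. Sample sizes and analyses are unchanged.

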#### Any Grade 2 ADR should be managed as follows:

- If a Grade 2 ADR resolves to Grade  $\leq$  1 by the last day of the current cycle, treatment may continue.
- If a Grade 2 ADR does not resolve to Grade ≤ 1 by the last day of the current cycle but it is manageable and / or not clinically relevant, the ADR should be discussed with the principal investigator and based upon discussion it is possible the infusion will be given on the following cycle. If at the end of the following cycle, the event has not resolved to Grade 1, discussion should be had with the principal investigator about permanently discontinuing treatment with M7824.

- Upon the second occurrence of the same Grade 2 ADR in the same subject (except for fatigue and hormone insufficiencies that can be managed by replacement therapy), continuation of treatment with M7824 has to be discussed with the principal investigator and might be permanently discontinued.
- Infusion-related reactions and hypersensitivity reactions (Grades 1 to 4) should be handled according to the guidelines provided in Sections **5.5.3.1 and 5.5.3.2**, respectively.
- Anemia should be handled according to the guidelines provided in Section **5.5.3.4**.

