#### 2.2.6.2 Immune-related Adverse Events / Autoimmune Disorders

Since inhibition of PD-L1 and TGF $\beta$  signaling stimulates the immune system, irAEs may occur. Treatment of irAEs is mainly dependent upon severity (NCI-CTCAE grade):

- Grade 1 to 2: treat symptomatically or with moderate dose steroids, more frequent monitoring
- Grade 1 to 2 (persistent): manage similar to high grade AE (Grade 3 to 4)
- Grade 3 to 4: treat with high dose corticosteroids

Treatment of irAEs should follow guidelines set forth in Section 5.5.3.3:

- Instructions for trial treatment discontinuation or interruption in case of irAEs / autoimmune disorders (see Section 5.5.3.3).
- Guidance for the medical management of irAEs / autoimmune disorders including specific guidance with regard to the affected organ / body system (see Section 5.5.3.3).
- irAEs / autoimmune disorders (any grade) are considered as AESIs requiring expedited reporting from the Investigator to Merck/EMD Serono. For non-serious AESIs, an AESI Report Form has to be completed; for serious events, an SAE Report Form has to be used.
- Regular laboratory tests on parameters indicative for autoimmune disorders will be performed as detailed in the Schedules of Assessments (see **Tables 1-3**).
- To help monitor for autoimmune effects, baseline ophthalmology examination including slit lamp inclusive of the anterior segment and including visual acuity. If clinically relevant eye signs or symptoms during the study, appropriate ophthalmology examination within 2 days including slit lamp inclusive of the anterior segment and including visual acuity.

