### 4.5 Criteria for Subject Withdrawal

#### 4.5.1 Withdrawal from Trial Treatment

Subjects will be withdrawn from trial treatment for any of the following reasons:

- PD as defined by iRECIST 1.1
  - Patients may continue on M7824 until immune confirmed PD (iCPD) provided they meet the criteria for pseudoprogression (see 5.5.1.1 below)
- Therapeutic failure requiring urgent additional cancer therapy
- Occurrence of any Grade ≥ 3 ADRs or repetitive Grade 2 ADRs as defined in Section 5.5.3.3.
- Occurrence of AEs, at the Investigator's discretion
- Pregnancy
- Use of prohibited concomitant drug, as defined in Section 5.5.2, where the predefined consequence is withdrawal from the IMP
- Non-adherence / non-compliance to the trial protocol or trial requirements (see Section 5.9)
- Withdrawal of consent
- Participation in any other trial

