#### 5.5.3.3 Immune-Related Adverse Events

For reporting irAE severity/toxicity grading, refer to CTCAE v4.03 toxicity grading system.

For treatment management of irAE per CTCAE v4.03 criteria, refer to American Society of Clinical Oncology (ASCO) Clinical Practice Guidelines and National Comprehensive Cancer Network irAE Management Guidelines.

Treatment of irAEs is mainly dependent upon severity as defined by NCI-CTCAE v4.03. In general, management by CTCAE v4.03 grading, as per ASCO, is listed below:

- Grade 1: study treatment should be continued with close monitoring, with the exception of some neurologic, hematologic, and cardiac toxicities.
- Grade 2: study treatment may be suspended for most Grade 2 toxicities, with consideration of resuming when symptoms revert to Grade 1 or less. Corticosteroids may be administered (initial dose of 0.5 to 1 mg/kg/day of prednisone or equivalent).
- Grade 3: study treatment is generally suspended and the high-dose corticosteroids (prednisone 1 to 2 mg/kg/day) or methylprednisolone 1 to 2 mg/kg/day) treatment should be initiated. Corticosteroids should be tapered over the course of at least 4 to 6 weeks. Some refractory cases may require infliximab or other immunosuppressive therapy.
- Grade 4: in general, permanent discontinuation of study treatment is recommended, with the exception of endocrinopathies that have been controlled by hormone replacement.

Since inhibition of PD-L1 stimulates the immune system, irAEs may occur. Treatment of irAEs is mainly dependent upon severity (NCI-CTCAE grade):

- Grade 1 to 2: treat symptomatically or with moderate dose steroids, more frequent monitoring
- Grade 1 to 2 (persistent): manage similar to high grade AE (Grade 3 to 4)
- Grade 3 to 4: treat with high dose corticosteroids

Treatment of irAEs should follow guidelines set forth in the ASCO/NCCN Management of Immunotherapy-Related Toxicities (https://www.nccn.org/professionals/physician\_gls/pdf/immunotherapy.pdf).

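### Sections 4.1.4.2 and 4.5.1 give conflicting rules for a recurrent Grade 2 adverse drug reaction, and 4.5.1 relies on a definition that Section 5.5.3.3 does not contain

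*Combined protocol and SAP*

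**What the plan says.** Section 4.1.4.2 has a block on Grade 2 ADRs. On the second occurrence of the same Grade 2 ADR in the same subject, "continuation of treatment with M7824 has to be discussed with the principal investigator and might be permanently discontinued". The block applies this to all such events "except for fatigue and hormone insufficiencies that can be managed by replacement therapy". For a Grade 2 ADR that has not resolved by the end of the cycle but is manageable and/or not clinically relevant, it asks for a discussion with the principal investigator; "based upon discussion it is possible the infusion will be given on the following cycle".

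Section 4.5.1 opens its list with "Subjects will be withdrawn from trial treatment for any of the following reasons". One of the reasons is any Grade 3 or higher ADR or "repetitive Grade 2 ADRs as defined in Section 5.5.3.3". No exemption is attached.

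Section 5.5.3.3 deals with immune-related adverse events (irAEs) grade by grade. At Grade 1, "Grade 1: study treatment should be continued with close monitoring", except for some neurologic, hematologic and cardiac toxicities. The next level reads "Grade 2: study treatment may be suspended for most Grade 2 toxicities, with consideration of resuming when symptoms revert to Grade 1 or less". A second short list, which also appears in Section 2.2.6.2, includes the line "Grade 1 to 2 (persistent): manage similar to high grade AE (Grade 3 to 4".

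**The concern.** A rule for stopping treatment should lead two readers to the same action for the same patient. Here one section leaves a recurrent Grade 2 ADR to a discussion and carves out two kinds of event. Another puts the recurrence on a list of reasons for which treatment stops, and refers the reader elsewhere for its meaning. If the place referred to is silent, the rule in 4.5.1 cannot be applied as written and the contradiction stays open.

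The consequences that the documents support are these:

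- The choice of section decides whether the patient receives further M7824.
- Section 6.1.2 bars from retreatment anyone whose toxicity led to discontinuation of the initial course, so the choice can also decide later access.
- Sections 7.5.3.1 and 7.5.3.3 summarize premature terminations by primary reason for treatment withdrawal, so the tabulated reasons depend on which rule was followed.

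**Working it through.** No arithmetic applies. The check sets the passages side by side.

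**Step 1. Recurrent Grade 2 ADR.**

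| | 4.1.4.2 | 4.5.1 | 5.5.3.3 |
|---|---|---|---|
| Trigger | Second occurrence of the same Grade 2 ADR | Repetitive Grade 2 ADRs | None stated for repeat events |
| Action | Discuss; discontinuation possible | Withdrawal from treatment | Suspension optional at Grade 2; resumption considered at Grade 1 or less |
| Exemptions | Fatigue; replaceable hormone insufficiency | None | None for Grade 2 recurrence |

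The first two columns differ in both action and exemptions.

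**Step 2. Can 4.5.1 be read as discretionary?** Its lead-in is mandatory. The same list has a separate entry for adverse events at the investigator's discretion. So where the list intends discretion it says so, and the Grade 2 entry does not.

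**Step 3. Does the cross-reference settle it?** Section 5.5.3.3 was read for a definition of a repetitive Grade 2 ADR. It has none. It does except endocrinopathies controlled by hormone replacement, but only from the Grade 4 recommendation to discontinue permanently. It also covers irAEs only, whereas 4.5.1 speaks of ADRs in general. Section 4.1.4.1 also sends the reader to Section 5.5.3 for discontinuation, withholding and restarting, without saying which section prevails if they differ.

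**Step 4. Trace one patient.** Take a second occurrence of Grade 2 hypothyroidism, related to M7824 and managed by replacement. The setting is realistic: Section 2.1.1 reports related Grade 1 or 2 hypothyroidism in 2 of the 19 dose-escalation subjects.

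- Under 4.1.4.2 the second-occurrence rule does not apply, because the event is exempt.
- Under 4.5.1, read literally, the subject is withdrawn from treatment.
- Under 5.5.3.3 no provision addresses the recurrence.

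**Step 5. Persistent Grade 1-2 irAE.** Sections 2.2.6.2 and 5.5.3.3 use the same line, so they agree with each other. Neither gives a duration for persistent. The neighboring lines concern symptomatic and steroid treatment, and 2.2.6.2 gives its pointer for discontinuation or interruption in a separate bullet. The line may therefore concern medical treatment only. If it is meant to cover dosing, its content is also unsettled: 4.1.4.2 requires discontinuation for Grade 3 ADRs with listed exceptions, while 5.5.3.3 describes Grade 3 as generally suspended.

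**The case against.** The strongest reply is that the conflict is a drafting slip with little practical effect. This is a single-institution trial, Section 1 has the Principal Investigator represent all investigators in decisions, and 4.1.4.2 already sends recurrent Grade 2 events to that role. The pointer in 4.5.1 may have been meant for 4.1.4.2, in which case the discretionary rule and its exemptions would be carried over. This is plausible and it limits how far practice would vary. It does not remove the defect: the text points elsewhere, and 4.5.1 as written leaves no room for the discretion that 4.1.4.2 grants.

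A reader might infer a wider conflict, in which one patient could be dosed, suspended, treated as Grade 3-4 or withdrawn depending on the section opened. The documents do not support that. On an unresolved Grade 2 event, 4.1.4.2 and 5.5.3.3 are both permissive. The first allows the next infusion after discussion, if the event is manageable and/or not clinically relevant; the second allows suspension for most such toxicities. They are compatible. The persistent-event line is most naturally read as steroid intensity, so it is an ambiguity and not a demonstrated contradiction about dosing.

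Infusion-related and hypersensitivity reactions and anemia have their own sections and lie outside the point.

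**Conclusion.** The point holds as an internal inconsistency. On a recurrent Grade 2 ADR, 4.1.4.2 is discretionary with two exemptions, 4.5.1 is mandatory with none, and the definition that 4.5.1 invokes is absent from 5.5.3.3. The undefined persistent-event line is a secondary ambiguity. The conclusion rests on a literal reading of the current text and on no numerical assumption. The sponsor should correct it, because it concerns when treatment stops.

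Its size cannot be given as a number. A reader might take the dose-escalation figures in Section 2.1.1 (9 of 19 subjects with a related event, 3 of them with one of Grade 3 or higher) and treat the remaining 9 - 3 = 6 of 19 as the share affected. That count includes subjects whose Grade 1-2 events occurred once and resolved. It leaves out subjects who had Grade 2 events alongside a Grade 3 event. It spans 0.3 to 20 mg/kg, whereas this trial gives a flat 1200 mg. The documents report no rate of recurrent Grade 2 ADRs.

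Nor do the documents show a bias in response rate, PFS or the Cohort B stage 1 decision. Sections 4.1.1.1 and 4.1.1.2 continue imaging until progression after a toxicity stop. Section 7.5.2.1.1 divides responders by all treated patients. Section 7.5.3.1 measures PFS from first dose to progression or death and states no censoring at withdrawal of treatment. Stopping a responder therefore does not by itself remove the response. An effect through lost exposure is possible but is not shown. The toxicity boundaries in Section 7.6 count related events of Grade 3 or greater, so a recurrent Grade 2 event does not enter them directly.

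**What to change.** Amend the protocol text as follows:

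1. Reconcile 4.1.4.2 and 4.5.1 into one rule for a recurrent Grade 2 ADR, and say what counts as repetitive.
2. State whether the exemptions for fatigue and replaceable hormone insufficiency apply under that rule.
3. Point the cross-reference in 4.5.1 to the section that holds the rule.
4. In 2.2.6.2 and 5.5.3.3, say what counts as persistent and whether the persistent Grade 1-2 line governs M7824 dosing or only medical treatment of the event.

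Which rule applies is for the sponsor's clinicians to decide; the review asks only that the sections agree. The cost is amendment wording, with no new data, visits or change to sample size.
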